2.2 Patients evaluable at 6-month follow-up

All enrolled patients meeting the following criteria will be considered evaluable at enrollment and at 6 month follow-up visit:

Patients considered evaluable at enrollment (i.e., responding to criteria of par 2.1 Full Analysis Set) who fulfill also the following criteria (i.e. all FAS patients who performed the 6-month follow-up visit and with at least one Treatment Satisfaction Questionnaire for Medication (TSQM-9) domain score calculated at the 6-month follow-up visit).

Criterion 11: Data collected at 6-month follow-up

- "Data collected at 6 (\pm 1) month follow up?" = "Yes" [F19_PATIENT_DISPOSITION, 6 month f-up.PD_1]

Criterion 12: Follow-up performed 6+/- 1 month from enrollment

- (Date of follow up visit (dd/mmm/yyyy) [F19_PATIENT_DISPOSITION, 6 month f-up.PD_2] – Date of enrolment visit (dd/mm/yyyy) [_PatientInfo. Date_enrollment]/30.4375 \geq 5) AND
- (Date of follow up visit (dd/mmm/yyyy) [F19_PATIENT_DISPOSITION, 6 month f-up.PD_2] – Date of enrolment visit (dd/mm/yyyy) [_PatientInfo. Date_enrollment] /30.4375 \leq 7)

The Biostatistician will evaluate the opportunity to apply a tolerance window during the analysis of data; the Sponsor will be informed of any possible changes in this range.

Criterion 13: patients with at least one Treatment Satisfaction Questionnaire for Medication (TSQM-9) domain score calculated at 6-month follow-up visit

- TSQM-9 items #1,2,3 [TSQM9_1-3] not missing & \neq "Non risponde" at 6-month follow-up, OR
- TSQM-9 items #4,5,6 [TSQM9_4-6] not missing & \neq "Non risponde" at 6-month follow-up, OR
- TSQM-9 items #7,8,9 [TSQM9_7-9] not missing & \neq "Non risponde" at 6-month follow-up

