9.3 VARIABLES

This is a non-interventional study and does not impose a therapy protocol, diagnostic/therapeutic procedure, or a visit schedule. Patients will be treated according to the local prescribing information, and routine medical practice in terms of visit frequency and types of assessments performed and only these data will be collected as part of the study.

This is a descriptive study, where patients with COPD, who are on treatment, are enrolled and evaluated during 12-months follow-up.

Exposure is defined as having diagnosis of COPD and being under treatment so in this study all enrolled patients are considered exposed.

The treating physician is asked to complete if possible at every patient visit the appropriate CRF.

Primary endpoint will be the patients' satisfaction to COPD medical treatments evaluated through the TSQM9 at baseline and at follow-up visits.

Secondary endpoints will be: patient disease perception (evaluated by means of illness perception questionnaire B-IPQ), adherence to COPD treatment (evaluated by means of MMAS4), health status (evaluated by means of CAT questionnaire) and dyspnea (evaluated by means of MMRC) during a 12-month observation period. Moreover, socio-demographic variables, smoking habits, medical history at baseline and lung function test results (by means of spirometry), COPD exacerbations, disease severity and medications for COPD, COPD exacerbations and adverse events during follow up will be collected. At each visit, each patient will fill in a structured interview aimed at assess his/her awareness of the disease.

Measurements of parameters will be performed by validated questionnaires or widely accepted instruments (e.g. spirometry).

Pulmonary function tests are a validated and well established measurement tool for lung function testing. Pulmonary function tests will be conducted at clinic visits using the site's

own equipment. FEV1, FVC, and DLCO are standard measurements for the assessment of lung function.

Finally, health care resources related to COPD, COPD exacerbations and adverse events will be evaluated during the observation period.

Table 1 below is the recommended assessment schedule that most likely mirrors the patterns of routine clinical care of most patients.

| Study Visits | Visit 1 | Visit 2 | Visit 3 |
|---|----------|-----------|-------------|
| | Baseline | Follow-up | Follow-up 2 |
| Months | 0 | 6 (+/-1) | 12 (+/- 1) |

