9.7 DATA ANALYSIS

Descriptive analysis will be means, medians, quantiles, proportions (with their respective 95% confidence intervals and SE when relevant) and contingency tables according to the nature of the variables. As a dispersion measurement the standard deviation and the interquartile range will be calculated.

Statistical analysis will be performed using the SAS software.

The statistical analysis will be done on all evaluable patients i.e. patients who enter the study without inclusion-exclusion criteria violations and with at least one TSQM-9 domain score (effectiveness, convenience and global satisfaction) calculated. Enrolled patients not evaluable for analysis will be described in terms of frequency of violations and according main socio-demographic variables (such as age and gender), clinical (such as disease severity and number of exacerbations in the 12-month before enrollment) and treatment satisfaction scores (if available) at baseline.

Patients with missing values will not be excluded from the analysis, their data will not be replaced; frequency of missing data will be given for all analyzed variables. Lost to follow up patients will be analyzed until their last available visit.

Appropriate descriptive statistics for main socio-demographic (gender, age, race, education and employment status, smoking habits) and clinical variables (medical history for COPD and not, disease severity and awareness) at baseline visit will be presented to describe the study population at inclusion. Patients at inclusion in the study will be also described in terms of ongoing pharmacological and non pharmacological treatments for COPD.

Moreover, the study population will be described in terms of number of exacerbations occurred during study period and changes in COPD medication since baseline.

The study objectives will be evaluated as below described.

Primary objective

The patients' satisfaction for medical treatment will be assessed by the 9-item Treatment Satisfaction Questionnaire for Medication (TSQM-9) at each study visit (45, 46). TSQM-9 is a self-rated tool for evaluating patient satisfaction to medical therapy. It is composed by 3 domains covering efficacy, convenience and global treatment satisfaction. TSQM-9 scores will be calculated according to author's instructions and summarized at each time point on all evaluable patients. Patients lost to follow up will be considered until their last available visit.

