2 DEFINITION OF EVALUABLE PATIENTS

2.1 Patients evaluable at enrolment (FULL ANALYSIS SET)

All enrolled patients meeting the following inclusion / exclusion / other criteria listed in the present paragraph will be considered evaluable at enrollment (Full analysis set) (i.e. COPD patients aged ≥ 40 years, with stable pharmacological treatment for COPD and no exacerbations for at least 3 months, who signed informed consent and privacy form, with at least one Treatment Satisfaction Questionnaire for Medication (TSQM-9) domain score calculated at enrollment visit):

Inclusion criteria

Criterion 1: Patients aged ≥ 40 years

- Question "1. Is the patient aged ≥ 40 years?" = "Yes" [\[F01_INC_EXC_CRITERIA.CI_1\]](#) AND
- Inclusion criterion "1. Patients aged ≥ 40 years?" not checked in the PROTOCOL DEVIATION FORM [\[F24_PROTOCOL_DEVIATION_FORM.PD_CI_1\]](#) AND
- Age at enrollment visit (years) ≥ 40 [\[_PatientInfo.Age\]](#)

Criterion 2: Patients must have a documented diagnosis of chronic obstructive pulmonary disease (COPD)

- Question "2. Has the patient a documented diagnosis of chronic obstructive pulmonary disease (COPD)?" = "Yes" [\[F01_INC_EXC_CRITERIA.CI_2\]](#) AND
- Inclusion criterion "2. Patients must have a documented diagnosis of chronic obstructive pulmonary disease (COPD)" not checked in the PROTOCOL DEVIATION FORM [\[F24_PROTOCOL_DEVIATION_FORM.PD_CI_2\]](#) AND
- Date of COPD diagnosis (mm/yyyy) not missing [\[F04_COPD_MEDICAL_HISTORY.MH_Date_diagnosis\]](#)

Criterion 3: Patients with no exacerbations in the last 3 months

- Question "3. Patient without any exacerbation in the last 3 months" = "Yes" [\[F01_INC_EXC_CRITERIA.QUESTION_3.CI_3\]](#) AND
- Inclusion criterion "3. Patients with no exacerbations in the last 3 months" not checked in the PROTOCOL DEVIATION FORM [\[F24_PROTOCOL_DEVIATION_FORM.PD_CI_3\]](#) AND
- Onset dates at each follow-up visit (Row 1 to 10) [\[F08_EXACERBATIONS.Ex_exacer_1-10_onset_date\]](#) > Date of enrolment visit (dd/mm/yyyy) [\[_PatientInfo.Date_enrollment\]](#)

Criterion 4: Patients requiring regular treatment according to GOLD guidelines, i.e.: undergoing stable pharmacological treatment for COPD since at least 3 months

- Question "4. Does the patient require a regular treatment according to GOLD guidelines, i.e.: undergoing stable pharmacological treatment for COPD since at least 3 months?" = "Yes" [\[F01_INC_EXC_CRITERIA.CI_4\]](#) AND

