2.3 Patients evaluable at 12-month follow-up

All enrolled patients meeting the following criteria will be considered evaluable at enrollment and at 12 month follow-up visit:

Patients considered evaluable at enrollment (i.e., responding to criteria of par 2.1 Full Analysis Set) who fulfill also the following criteria (i.e. all FAS patients who performed the 12-month follow-up visit and with at least one Treatment Satisfaction Questionnaire for Medication (TSQM-9) domain score calculated at the 12-month follow-up visit).

Criterion 14: Data collected at 12-month follow-up

- "Data collected at 12 (\pm 1) month follow up?" = "Yes" [F19_PATIENT_DISPOSITION, 12 month f-up.PD_1]

Criterion 15: Follow-up performed 12+/- 1 month from enrollment

- (Date of follow up visit (dd/mmm/yyyy) [F19_PATIENT_DISPOSITION, 12 month f-up.PD_2] – Date of enrolment visit (dd/mm/yyyy) [_PatientInfo. Date_enrollment]/30.4375 \geq 11) AND
- (Date of follow up visit (dd/mmm/yyyy) [F19_PATIENT_DISPOSITION, 12 month f-up.PD_2] – Date of enrolment visit (dd/mm/yyyy) [_PatientInfo. Date_enrollment] /30.4375 \leq 13)

The Biostatistician will evaluate the opportunity to apply a tolerance window during the analysis of data; the Sponsor will be informed of any possible changes in this range.

Criterion 16: patients with at least one Treatment Satisfaction Questionnaire for Medication (TSQM-9) domain score calculated at 12-month follow-up visit

- TSQM-9 items #1,2,3 [TSQM9_1-3] not missing & \neq "Non risponde" at 12-month follow-up, OR
- TSQM-9 items #4,5,6 [TSQM9_4-6] not missing & \neq "Non risponde" at 12-month follow-up, OR
- TSQM-9 items #7,8,9 [TSQM9_7-9] not missing & \neq "Non risponde" at 12-month follow-up

Three sets of patients have been identified for the evaluation of SAT study objectives. Chart 1 displays the analysis sets considered for the statistical analyses foreseen in the Study Protocol.

Chart 1: Sets of patients considered for each statistical analysis

| | Patients evaluable at enrollment (FAS) | Patients evaluable at enrollment and at 6 month follow-up | Patients evaluable at enrollment and at 12 month follow-up |
|--|---|--|---|
| Enrolled and evaluable patients | X | X | X |
| Main socio-demographics and life habits (age, gender, race, education, employment status) at enrollment | X | | |
| Medical history for COPD (number of exacerbations in the 12 months prior to enrollment) | X | | |

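### The SAP narrows the protocol's evaluable population without declaring it (baseline TSQM-9 required, ±1 month used as an exclusion rule) and leaves the visit tolerance to be settled during analysis

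*SAP*

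**What the plan says.** **Protocol.** Section 9.7 defines the evaluable population as "patients who enter the study without inclusion-exclusion criteria violations and with at least one TSQM-9 domain score", with no visit attached. It adds "Patients with missing values will not be excluded from the analysis, their data will not be replaced" and "Lost to follow up patients will be analyzed until their last available visit". For secondary objective #2 the repeated-measures models are to draw on every available value. Section 9.3 says the study "does not impose a therapy protocol, diagnostic/therapeutic procedure, or a visit schedule", but it also gives 6 (±1) and 12 (±1) months as the times of data collection.

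**SAP.**
- Criterion 10 (section 2.1) admits a patient to the FAS only with a "domain score calculated at enrollment visit".
- Sections 2.2 and 2.3 build the 6- and 12-month sets inside the FAS.
- Criterion 12 requires the 6-month visit to fall at 5–7 months. Criterion 15, "Follow-up performed 12+/- 1 month from enrollment", requires 11–13 months.
- Both sections add that "The Biostatistician will evaluate the opportunity to apply a tolerance window during the analysis of data". The sponsor is only to be told of any change.
- Section 4.3 uses these visit-specific sets as denominators for the primary Tables 10 and 11. Section 4.9 restricts the mixed models (Tables 17–19) to 12-month evaluable patients, and Chart 1 does the same for the correlation analysis (Table 37).

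Section 4.9 openly states that it departs from the protocol on post-baseline covariates. No such statement accompanies the evaluability rules.

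**The concern.** The two documents define different populations for the primary endpoint, and the later one is smaller. A patient who skipped the baseline questionnaire but completed it at 6 and 12 months is evaluable under the protocol and excluded under the SAP. A patient seen a few days late is evaluable at that visit under the protocol and not under the SAP. If people who attend late or leave questionnaires blank differ in satisfaction from those who do not, the reported means describe a selected group.

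The tolerance sentence adds a second problem. This is a single open cohort, so the person deciding whether late visits count can already see the scores. A population rule should be settled before that point.

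**Working it through.** **1. Who is lost, and from what.**

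| Patient | Protocol 9.7 | SAP |
|---|---|---|
| No baseline score, valid 6- and 12-month scores | Evaluable | Out of the FAS and both nested sets, so out of Tables 4–39; can remain in Tables 1–3 and 40–44 |
| 6-month visit out of window, 12-month visit in window | Evaluable at all visits | Out of the 6-month columns of Tables 10–16 |
| 12-month visit out of window, earlier visits valid | Evaluable at all visits | Out of the 12-month columns of Tables 10–16, and out of Tables 17–19 and 37 altogether |

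In the third row the models lose valid baseline and 6-month scores as well as the late one, which conflicts with the protocol's use of all available values.

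**2. The window in days.** As printed, criteria 12 and 15 divide only the enrolment date by 30.4375; I read them as dividing the date difference. The limits are then 5 × 30.4375 = 152.2 to 7 × 30.4375 = 213.1 days, and 11 × 30.4375 = 334.8 to 13 × 30.4375 = 395.7 days. A visit at 13.1 months is 13.1 × 30.4375 = 398.7 days, about 3 days too late.

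**3. The protocol's precision table.** Inputs from Protocol 9.5: 400 enrolled, drop-out 5% or 20%, SD 21.4 (mean 54.4) or 16.6 (mean 79.7). N = 400 × 0.95 = 380 or 400 × 0.80 = 320; SE = SD/√N; half-width = 1.96 × SE.
- SD 21.4: N = 380 gives SE 1.098, half-width 2.152; N = 320 gives 1.196 and 2.345.
- SD 16.6: N = 380 gives 0.852 and 1.669; N = 320 gives 0.928 and 1.819.

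All eight figures match Table 2 of the protocol.

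**4. Precision if more patients are lost.** The share removed by criteria 10, 12 and 15 is not in the documents. I assume 10–30% off 320. This is a deliberately harsh case, because 320 already allows for non-evaluable patients.

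| Further loss | n | Half-width, SD 21.4 (% of 54.4) | Half-width, SD 16.6 (% of 79.7) |
|---|---|---|---|
| 0% | 320 | 2.345 (4.31%) | 1.819 (2.28%) |
| 10% | 288 | 2.472 (4.54%) | 1.917 (2.41%) |
| 20% | 256 | 2.621 (4.82%) | 2.033 (2.55%) |
| 30% | 224 | 2.802 (5.15%) | 2.174 (2.73%) |

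The protocol's own benchmark is a relative error below 30%.

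**5. Possible selection shift.** Retained mean minus mean of all otherwise evaluable patients = share excluded × (retained mean − excluded mean). With an assumed difference of 10 points:
- 5% excluded: 0.05 × 10 = 0.5 points
- 10%: 1.0
- 20%: 2.0
- 30%: 3.0

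Assumed differences of 5 and 15 points give 0.25–1.5 and 0.75–4.5 points over the same shares. With a 10-point difference and 20–30% excluded, the shift is about as large as the half-widths in step 4; at 5–10% it is well below them. The documents support neither a size nor a direction for the difference.

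**The case against.** The best defence is that ±1 month is the protocol's own timing, and that the primary objective concerns satisfaction after 6 and 12 months. Restricting those columns to visits near those times is a reasonable choice. That stands: the SAP did not invent the window. What is new is its use to exclude patients.

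The defence also limits several stronger readings that a reader might infer:
- *Criterion 10 removes patients from every later table.* It does not. The safety set (SAP 2.4) does not require it, and Tables 1–3 count all enrolled patients. Patients with late visits also stay in the FAS tables on resource use, treatments and exacerbations.
- *Collected scores will certainly be thrown away.* The documents do not show this. Criteria 11 and 14 rest on an eCRF question that itself contains ±1 month, and nothing says how sites answer it, or whether they enter a TSQM-9, when a visit is late.
- *The window could be tuned to favourable results.* A tolerance most naturally widens the range, which moves back towards the protocol, and the primary analysis is descriptive with no comparison or test. What stands is that its size, trigger and deadline are not set.
- *The study loses its precision.* Step 4 of the working shows otherwise.

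Criterion 10 has some logic too: it asks for only one of three domains, and change from enrolment needs a baseline value. That justifies restricting the change columns, but not removing the patient from the visit means or from exacerbation and hospitalisation counts.

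Finally, Table 2 of the SAP lists reasons for non-eligibility, and section 4.2 allows baseline characteristics to be compared across sets to look for selection bias. That comparison is optional, and because it starts from the FAS it cannot show who was lost through criterion 10.

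**Conclusion.** The point holds as an undeclared narrowing of the protocol's population with an open-ended tolerance. It should be corrected. The conflict between the definitions follows from the text alone and needs no assumption.

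Its numerical effect cannot be known from the documents. Under the assumed ranges, precision is hardly touched (relative error at most 5.15%), while the mean could shift by 0.5–3.0 points if excluded and retained patients differ by 10 points. The most clear-cut loss is in Tables 17–19, where one late or missing 12-month visit removes valid earlier scores that the protocol says to use.

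**What to change.** 1. Define the FAS as no eligibility violation plus one or more domain scores at any visit. Report change from enrolment where a baseline score exists.
2. In Tables 10–11 include every TSQM-9 score collected at the nominal 6- and 12-month visits, and reword criteria 11 and 14 so that they do not bring the window back in.
3. Fit the models for Tables 17–19 on all FAS patients with any available score, and remove the restriction to 12-month evaluable patients.
4. Keep the ±1 month set as a pre-specified sensitivity analysis, with the bracket in its date formula corrected.
5. Delete the tolerance sentences in SAP 2.2 and 2.3.

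If the sponsor prefers the window as the main analysis, it should fix the window and any tolerance before database lock, declare the departure from Protocol 9.7, and make the all-visits analysis the sensitivity analysis.

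The cost is SAP rewording, reprogrammed evaluability flags, changed denominators in the FAS-based tables and one added sensitivity analysis. Visit times in the main analysis will spread more widely, so their distribution should be reported. No new data collection is required.

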2.3 Patients evaluable at 12-month follow-up

All enrolled patients meeting the following criteria will be considered evaluable at enrollment and at 12 month follow-up visit:

Patients considered evaluable at enrollment (i.e., responding to criteria of par 2.1 Full Analysis Set) who fulfill also the following criteria (i.e. all FAS patients who performed the 12-month follow-up visit and with at least one Treatment Satisfaction Questionnaire for Medication (TSQM-9) domain score calculated at the 12-month follow-up visit).

Criterion 14: Data collected at 12-month follow-up

- "Data collected at 12 (\pm 1) month follow up?" = "Yes" [F19_PATIENT_DISPOSITION, 12 month f-up.PD_1]

Criterion 15: Follow-up performed 12+/- 1 month from enrollment

- (Date of follow up visit (dd/mmm/yyyy) [F19_PATIENT_DISPOSITION, 12 month f-up.PD_2] – Date of enrolment visit (dd/mm/yyyy) [_PatientInfo. Date_enrollment]/30.4375 \geq 11) AND
- (Date of follow up visit (dd/mmm/yyyy) [F19_PATIENT_DISPOSITION, 12 month f-up.PD_2] – Date of enrolment visit (dd/mm/yyyy) [_PatientInfo. Date_enrollment] /30.4375 \leq 13)

The Biostatistician will evaluate the opportunity to apply a tolerance window during the analysis of data; the Sponsor will be informed of any possible changes in this range.

Criterion 16: patients with at least one Treatment Satisfaction Questionnaire for Medication (TSQM-9) domain score calculated at 12-month follow-up visit

- TSQM-9 items #1,2,3 [TSQM9_1-3] not missing & \neq "Non risponde" at 12-month follow-up, OR
- TSQM-9 items #4,5,6 [TSQM9_4-6] not missing & \neq "Non risponde" at 12-month follow-up, OR
- TSQM-9 items #7,8,9 [TSQM9_7-9] not missing & \neq "Non risponde" at 12-month follow-up

Three sets of patients have been identified for the evaluation of SAT study objectives. Chart 1 displays the analysis sets considered for the statistical analyses foreseen in the Study Protocol.

Chart 1: Sets of patients considered for each statistical analysis

| | Patients evaluable at enrollment (FAS) | Patients evaluable at enrollment and at 6 month follow-up | Patients evaluable at enrollment and at 12 month follow-up |
|--|---|--|---|
| Enrolled and evaluable patients | X | X | X |
| Main socio-demographics and life habits (age, gender, race, education, employment status) at enrollment | X | | |
| Medical history for COPD (number of exacerbations in the 12 months prior to enrollment) | X | | |
| Patients' satisfaction to COPD medical treatments (by means of the TSQM9) at each study visit | X* | X* | X* |
| Patient disease perception (by means of illness perception questionnaire B-IPQ) at each study visit | X* | X* | X* |
| Patient adherence to COPD treatment (by means of MMAS4) at each study visit | X* | X* | X* |
| Patient health status (by means of CAT questionnaire) at each study visit | X* | X* | X* |
| Measurement of dyspnea (by means of mMRC) at each study visit | X* | X* | X* |
| Patient's COPD awareness (COPD awareness questionnaire) at each study visit | X* | X* | X* |
| Relation between treatment satisfaction and demographic (such as age, gender), clinical (such as number of exacerbations, spirometric parameters) parameters and PROs during a 12-month observation period | | | X |
| Description of health care resources utilization and related cost according to the Italian National Health Service (INHS) during a 12-month observation period. | X | | |
| To assess the correlation between patients' satisfaction and resource utilization during a 12-month observation period | | | X |
| Ongoing pharmacological and non-pharmacological treatments for COPD | X | | |
| Exacerbations occurred during observation period | X | | |

*Patients having PRO score computable at the visit will be considered for this analysis (i.e. PRO filled in at the visit and having a sufficient number of items recorded to allow score computation (PROs computation details are reported in Section 3. "Computed Variables"))).

